The stress reactivity paradigm includes two imagery conditions (neutral-relaxing, stress related) and a laboratory session. This paradigm will be completed at pre- and post-treatment assessments. During a visit prior to laboratory sessions, participants will complete two Scene Development Questionnaires (Sinha & Tuit, 2012) that are designed to collect information about each imagery condition (a non-drug-related stressful event in their life, and a neutral-relaxing event); scripts for the imagery conditions will be developed using the information collected. Each script will be written, recorded, and edited by trained research staff in order to ensure that scripts are standardized in terms of length and content. During laboratory sessions, participants will listen to each script. The order of the scripts will be randomized. Psychophysiological measures (skin conductance) will be collected before, during, and after each imagery script. Skin conductance response will be collected using a Biopac MP150 system running AcqKnowledge 4.4 software (Biopac Systems Inc., USA) and the Biopac electrodermal activity amplifier (EDA100c). Skin conductance response is used as an index of physiological arousal, and therefore stress reactivity. Subjective measures that will be administered prior to and following each imagery condition include the Positive and Negative Affect Scale (Watson, Clark, & Tellegen, 1988), and the Opioid Craving Scale (Weiss et al., 2003) that has been adapted to assess craving in the present moment (i.e., “right now”). Following each imagery script participants will also be asked to rate how “clearly and vividly” they were able to imagine the scenario on a 10-point visual analog scale.

V.4.4. Urine Toxicology

Participants will provide weekly urine samples to screen for drug use. Although opioid use is the primary outcome for this trial, the presence of other substances of abuse will be used as secondary outcome. We will use the Alere Toxicology iCup 13 panel drug test screening cup, which tests for the presence of the following substances: cocaine, marijuana, opiates, amphetamines, methamphetamines, phencyclidines, benzodiazepines, barbiturates, methadone, tricyclic antidepressants, oxycodone, propoxyphene, and buprenorphine. We will also use a Drug Screen Test Dip Card to test for fentanyl in the urine sample.

V.4.5. Measurement of Sex Hormones and Menstrual Cycle Phase

Female participants will provide saliva samples and will report descriptive data on menstrual cycle phase in order to measure fluctuations in estradiol and progesterone throughout the study period. Salivary assays of estradiol and progesterone will be performed in duplicate and in

accordance with manufacturer specifications at the Laboratory for Biological Health Psychology at Brandeis University. Saliva samples will be collected using the passive drool method and according to recommended collection procedures. Samples will be collected at baseline (immediately prior to the Escape Go/NoGo Task) and at each weekly session. In addition to measurement of salivary estradiol and progesterone, we will also collect descriptive data on menstrual cycle phase (with the Menstrual Cycle Information form), following recommendations for optimizing measurement of menstrual phase (Allen et al., 2016). Specifically, we will utilize both self-reported onset of menses and weekly hormone data to characterize menstrual cycle phase throughout the trial. We will also assess for presence, type, dose, and compliance with birth control at each time point. Furthermore, using the interviewer-administered Saliva Sample Activity Documentation form, we will collect information on participant activity in the past 12 hours that may affect saliva collection.

VI. BIOSTATISTICAL ANALYSIS

Data from this randomized controlled trial will be analyzed using descriptive and qualitative analytic methods as well as traditional significance tests. Measures of patient satisfaction will be considered along with qualitative exit interviews to determine the acceptability of the treatment. Randomized groups will be compared with respect to baseline demographic and clinical variables using t-tests and chi-square tests; if significant group differences are identified in any variables known to be highly predictive of outcome, these variables will be adjusted for via their inclusion as covariates. These covariates will also be summarized with descriptive statistics and graphical methods to determine the most appropriate way to incorporate them in the analyses (e.g., continuous or categorical representation). All outcome analyses will utilize an intent-to-treat approach, complemented by exploratory completer analyses.

The hypothesis that I-CBT will yield greater reduction in opioid use and anxiety symptoms will be tested using separate linear mixed effects models for opioid use (weeks of use in the previous 4 weeks) and anxiety (HARS score) examining the main effect of treatment condition and its interaction with time on each outcome. The correlation among the repeated measures of the dependent variable will be appropriately accounted for via the inclusion of random subject effects (e.g., random intercepts and slopes for time). Covariates will include pre-treatment values of the dependent variable and any baseline demographic or clinical variables identified as necessary covariates in preliminary analyses.

To test the hypothesis that baseline stress reactivity is associated with treatment outcome at post-treatment (week 12), linear regressions will be utilized with primary opioid and anxiety outcomes at week 12 as the dependent variables and post-stress task anxiety, craving, and heart rate variability as independent variables, co-varying for baseline severity and any other covariates identified in preliminary analyses. In addition, to test the hypothesis that reduction in stress reactivity over time will be greater in the I-CBT condition, a linear mixed effects model will be conducted examining whether stress reactivity decreased from pre- to post-treatment and whether groups differed with respect to this change; this analysis will include the main effects of time and group and the time x group interaction. The correlation among repeated measures of the dependent variable will be accounted for via the inclusion of random subject effects.

With repeated assessments over 7 months of study participation, some amount of missing data is inevitable. Extensive efforts will be made throughout all stages of follow-up to minimize missing data by vigorous outreach, including to any participants who elect to dropout of treatment prior to completion. For all of the proposed analyses, we will use statistical methods (e.g., linear

mixed effects models) that incorporate partially observed data on participants who are lost to follow-up.

We do not expect more than a 10% loss to follow-up (see C.4); nonetheless, the sample size of 54 participants was selected to provide adequate degrees of freedom to estimate the treatment effect size and its reliability, even when allowing for up to 20% loss to follow-up. In this Stage 1 trial, we will focus on the estimation of effect sizes and clinically-significant change (as defined by Jacobson & Truax, 1991). If promising results (i.e., presence of clinically-significant change) are detected, these data will provide an estimate of the reliability of the effect to inform power calculations for a larger Stage 2 clinical trial. Although the focus of this trial is the estimate of an effect size and its reliability, we have conducted a power analysis for the proposed sample size; effect sizes are expressed as standardized differences in means for ease of interpretation. For Aim 2, based on unpublished data from previous clinical trials, we anticipate a small correlation between repeated measures of the opioid use outcome ($r < .20$) and a small to medium correlation ($r = 0.42$) for the HARS. Thus, the proposed sample size would provide adequate power (power of at least 0.80) to detect a minimum between-group difference from baseline to end of treatment in the magnitude of a large effect size ($d = .70-.75$). For Aim 3, based on previous studies examining stress reactivity and alcohol and cocaine use following treatment, which have consistently reported medium to large effect sizes (Sinha et al., 2009; 2011), the proposed sample size would provide adequate degrees of freedom to detect an effect size in the range of high medium to large.

VII. RISKS AND DISCOMFORTS

The anticipated risks associated with the proposed study are minimal. As in any study involving assessment of psychiatric symptoms, there is some risk of emotional discomfort from discussing emotional topics (e.g., symptoms of anxiety, substance use). However, this discomfort is expected to be transient. In addition, the stress reactivity tests are designed to elicit mild to moderate, transient distress. Accordingly, evidence suggests that completion of laboratory stress-reactivity paradigms is not associated with increased risk of subsequent substance use (DeSantis et al., 2009). Participants will be monitored by study staff. If a participant reports experiencing, (or study staff observes) distress at a higher level or longer duration than the mild to moderate, transient distress anticipated in study procedures, the PI will be contacted to determine whether intervention or withdrawal is indicated.

Presence of any of the following criteria throughout the study will trigger a review of the participant's appropriateness for the study by the study PI in consultation with at least one other clinical provider (either a clinician on the research team, or another member of the patient's treatment team, if a release of information has been provided): (1) any serious adverse event, (2) evidence for a significant worsening of clinical status as indicated by (a) 2 consecutive weeks of a positive urine toxicology screen (not including prescribed medications or marijuana), or (b) 2 consecutive weeks of no-showing study treatment sessions.

A core component of cognitive behavioral approaches to anxiety disorders is exposure to feared stimuli (e.g., social interactions, heights). This approach is intended to elicit moderate levels of anxiety in order for extinction of fear responding (the purported mechanism of change) to occur. Accordingly, this procedure has consistently demonstrated efficacy across the range of anxiety disorders for symptom reduction and disorder remission (e.g., Barlow et al., 2000). These

procedures are expected to elicit moderate levels of anxiety, which are similar to the anxiety experienced by individuals with elevated anxiety symptoms in daily life. Evidence from numerous large-scale clinical trials supports the safety and tolerability of these procedures, as indicated by high retention rates (see Hembree et al., 2003) and high levels of patient satisfaction (e.g., Stein et al., 2011), including in substance-dependent samples (e.g., Mills et al., 2012; Otto et al., 2010). Nonetheless, subjects will be closely monitored for evidence of excessive or enduring distress following these procedures and precautions to protect against this risk will be taken.

Another potential risk includes the possibility that subjects may experience dangerous or suicidal behavior. These are possible because of the nature of the dually diagnosed population studied in this research. We do not anticipate that our study procedures will increase this particular risk, but there is a risk that this could occur during the study period. If a subject becomes very upset, is intoxicated, or is suicidal during the study, he or she will be seen by one of the study clinical staff members. An assessment will be conducted, and the appropriate clinical recommendation will be made; this could involve treatment either at McLean Hospital or elsewhere. If a patient provides a positive breath alcohol screen, a member of the study clinical staff will meet with the patient to determine whether he/she is able to complete the clinical or research session and to determine the participant's safety level and appropriate next steps (e.g., send to emergency room, refer to detox, send home in taxi, send home with a friend, etc.).

Accidental opioid overdose, including fatal overdose, is a possible outcome of opioid use disorder. We do not believe study procedures will increase this particular risk, because treatment enrollment has been found to be protective against overdose-related mortality among opioid-dependent individuals (Degenhardt et al., 2011). In addition, all participants are required to be on pharmacotherapy for opioid dependence which is robustly associated with a decreased risk of overdose in this population (Volkow et al., 2014). As noted above, all participants will be closely monitored and appropriate level of care will be re-evaluated if there is evidence of a worsening of clinical status.

Another potential risk is a breach of confidentiality. However, as with the other risks mentioned above, we will take precautions to protect against this risk. Participants will receive a copy of the informed consent form explaining their privacy and confidentiality. All data will be coded with a unique identifier and will be stored separately from any identifying information (i.e., informed consent forms, clinical charts). Given the longitudinal nature of this clinical trial, a key linking the unique subject identifier to the participant's name will be maintained. This will be stored on password protected computer and a locked cabinet separate from other data. Informed consent forms and data will be stored separately in locked files and only research staff will have access to this information. Electronic questionnaires will be stored in the Redcap Database. As noted above, Redcap is an encrypted, electronic database that is both HIPPA compliant (Health Insurance Portability and Accountability Act) and approved by Partners IRB for the administration and storage of human subject information (for addition information on the RedCap Database feature see <http://rc.partners.org>). Only research staff affiliated with this proposal will have access to any identifying information. Data being analyzed will not include identifying information. The identity of the participants will not be revealed in the presentation or publication of any result from the project. To provide additional privacy protection given the sensitive nature of the data collected (e.g., substance use data), a certificate of confidentiality will be requested from the National Institute on Drug Abuse. This will be requested following IRB approval, consistent with NIDA procedures.

Participants will be fully informed of the nature of the risks involved during the informed consent process and will have the ability to discontinue and withdraw consent at any time. All study personnel will be trained in the appropriate care of human participants, and will have completed the National Cancer Institute (NCI) course, Human Participants Protections Education for Research Teams, and research assistants will be closely supervised by the study PI. As part of the informed consent process, participants will be informed that if they feel uncomfortable responding to any question that they are free to choose not to respond or to express their discomfort. Each participant will be made aware that participation is completely voluntary and that he or she may withdraw participation at any time without penalty.

VIII. POTENTIAL BENEFITS

The major potential benefit to participants is the receipt of treatment that might help them to achieve their goals of maintaining abstinence from opioids and reducing anxiety. Participants will receive free cognitive behavioral treatment as part of this study from providers experienced in treating substance dependence. Participants also will receive the potential benefit of participating in a study that may contribute to establishing more effective treatment for patients with co-occurring opioid dependence and anxiety disorders. Given the minimal risks associated with the proposed investigation, we believe that this is a very acceptable risk-benefit ratio.

IX. MONITORING AND QUALITY ASSURANCE

The PI will have responsibility for continuous monitoring of the data and safety of subjects in the study. Further consultation will be obtained if necessary from the McLean Hospital Office of Research Administration.

Continuous, close monitoring of safety issues by the PI will take place throughout the study's duration with prompt reporting of adverse events to the Partners IRB. At the time of annual, continuing review we will provide the Partners IRB with a summary of any unexpected and related adverse events as well as any other unanticipated problems that occurred since the last continuing review. We will also follow the Partners IRB policies for expedited reporting of Adverse Events and Serious Adverse Events.

IX.1. Reporting Unanticipated Problems Including Adverse Events (AEs) and Serious Adverse Events (SAEs)

Tracking of Unanticipated Problems including AEs will begin at the time of consent. Unanticipated Problems including AEs will be assessed at every research assessment and treatment session (i.e., baseline, weeks 1-12, post-treatment, 1-month follow-up, and 3-month follow-up). At every study appointment, research staff will ask about any emergency room visits, inpatient admissions, etc. (see Unanticipated Event Form). In addition, participants will be closely monitored during study assessment and treatment for any psychological distress or adverse reactions to any treatment procedures and study clinicians will assess for suicidal behavior or increased severity of psychological distress. Study staff will follow the guidelines below to determine how to report and categorize Unanticipated Problems. Any AE that results in hospitalization or death will be reported to the IRB within 24 hours and will be categorized as an SAE. We will consult the IRB for guidance on any event not outlined in the protocol that are possibly related to study participation. Events that are unrelated to the disorder or study participation will not be collected in the present study given that it is a psychotherapy trial (e.g., common medical illness, such as cold or flu).

	Reporting Procedure	Data Collection Form(s)
Unanticipated problems possibly related to study participation: 
 • Unanticipated psychological stress following treatment procedures • Adverse Reactions to Physiological equipment 	Report to the PHRC IRB	Unanticipated Event Form, note as Adverse Event
Other Unanticipated Problems that are possibly related to study participation: 
 • Breaches of confidentiality 	Report to the PHRC IRB	Research progress note
Unanticipated problems related to the course of the clinical disorder being treated not related to study participation, including such examples as: 
 • Drug overdose • Suicidal ideation/suicide attempt • Increase severity of psychological distress requiring medical/psychiatric attention • Participation incarceration 	Report to PHRC IRB	Unanticipated Event Form, consult with IRB to determine whether Adverse Event or Unanticipated Problem
Hospitalization	Report to PHRC IRB	Unanticipated Event Form, consult with IRB to determine whether Adverse Event or Unanticipated Problem

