This study seeks to extend and adapt transdiagnostic treatment for anxiety disorders into a novel integrated cognitive behavioral treatment (ICBT) for co-occurring opioid dependence and anxiety disorders. Given the absence of treatment research in this population, this study has the potential to advance the field by providing information on the efficacy of a standard versus a novel behavioral treatment approach. From a public health perspective, the development of treatments that target multiple disorders has the potential to enhance efforts to increase access to evidence-based treatments by substantially reducing the training and implementation burden on treatment settings (McHugh et al., 2009). An integrated treatment extending this transdiagnostic approach to include both anxiety disorders and co-occurring opioid dependence would have wide applicability, even if more than one anxiety disorder or substance dependence diagnosis is present.

II. SPECIFIC AIMS

Anxiety disorders are highly prevalent in opioid-dependent individuals and confer risk for poor response to treatment. Opioid dependence and anxiety disorders share a number of overlapping and interacting features that may contribute to the maintenance of both chronic anxiety and opioid use. For example, anxiety is among the most commonly reported motives for opioid use, and both disorders are characterized by elevated intolerance of distressing internal states (distress intolerance). However, despite the high prevalence and poor prognostic impact of anxiety disorders on opioid dependence, little is known about treating these co-occurring conditions.

Given the overlapping and interacting nature of symptoms, this population may be best served by integrated treatment approaches targeting both conditions simultaneously. To address this notable need, the overarching aim of the proposed study is to test an integrated cognitive behavioral treatment for co-occurring opioid dependence and anxiety disorders.

Specific Aim 1. To examine the feasibility and acceptability of an integrated cognitive behavioral treatment manual for opioid dependence and anxiety disorders (ICBT). We hypothesize that ICBT will be a feasible and acceptable treatment as assessed by the ability to recruit and retain the target population and participant self-report of treatment satisfaction.

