Potentially eligible subjects will be asked to complete the Informed Consent process, at which point the subjects will read through the IRB-approved consent form, and will meet with a research staff member who will answer any questions, explain the schedule of study procedures, and review the risks and benefits of the study. Subjects will be informed about the experimental nature, purpose, risks, and benefits of the study in accordance with procedures of the Partners IRB. There will be no time-limit placed on the consenting process. Research staff members understand that the consent is a process and not simply a matter of signing and dating the consent form. Either the PI or one of the Co-Investigators (serving as designees of the PI) will be available to help explain the study and answer questions. Once the subject consents to participate in the study, the subject will sign and date the consent form along with a member of the research staff. The subject will be provided with a copy of the consent form and the original will be stored in a secure location by a member of the study staff.

Participants will be randomly assigned to receive either ICBT or IDC. This randomization will be stratified by the following variables: (1) presence of a medication for anxiety, (2) gender, (3) type of opioid medication (agonist/partial agonist vs. antagonist), and (4) severity (defined by presence vs. absence of opioid use since initiating pharmacotherapy for opioid use).

V. STUDY PROCEDURES

All participants will receive 12 individual weekly sessions of ICBT or IDC and will complete assessments at baseline, week 12, and 1- and 3-month post-treatment follow-up visits. Breath alcohol screens will be conducted at each session and assessment visit to confirm absence of acute alcohol use. Procedures for response to a positive breathalyzer screen are specified below in Section VII. Qualitative exit interviews will be conducted at the completion of treatment. These interviews will focus on issues related to feasibility and acceptability, such as identifying the most and least helpful sessions and areas for improvement. Details of the procedures are included below.

V.1. Eligibility and Baseline Assessment

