symptom and disorder severity. The previous version of the ADIS for DSM-IV demonstrated good to excellent reliability for most DSM-IV categories (Brown et al., 2001). The shorter current diagnosis version of the ADIS (Mini-ADIS) will be administered at all assessments.

Anxiety Sensitivity Index (ASI). The ASI (Peterson & Reiss, 1992) is a self-report instrument designed to assess one's tendency to respond fearfully to anxiety-related symptoms. For each statement, respondents rate each item on a Likert scale ranging from very little (0) to very much (4). The ASI total score is computed by summing responses across the 18 items. Data on the reliability and validity of the ASI scales have been favorable (e.g. Reiss et al., 1986). An updated and validated version of the ASI will be used in this study (Taylor et al., 2007).

Brief Pain Inventory - Short Form (BPI). The BPI (Cleeland, 1989) is a 9-item self-report measure of pain and pain-related functional interference. The BPI is a widely used measure of pain that has demonstrated strong internal consistency reliability and construct validity in diverse patient samples for both the long (e.g., Gjeilo et al., 2007; Tan et al., 2004) and short forms (Mendoza et al., 2006). This measure will be used to examine pain and pain interference. The BPI will be administered at baseline, post-treatment, and 3-month follow-up.

Client Satisfaction Questionnaire (CSQ). The CSQ (Larsen et al., 1979), an 8-item self-report measure of treatment satisfaction, will be administered at post-treatment.

Concomitant Treatment Questionnaire (CTQ). Participants will be asked to report on any current treatment in addition to the study treatment for substance use or psychiatric problems.

Credibility and Expectancy Scale (CES). The CES (Borkovec & Nau, 1972) is a measure of the degree to which participants anticipate a therapy will be helpful for their symptoms and the degree to which it is credible. This measure will be administered at sessions 3 and 7 as a measure of feasibility.

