Distress Intolerance Index. The Distress Intolerance Index (DII; McHugh & Otto, 2011) is a 10-item self-report measure of the intolerance of distressing states that was derived from a study of distress intolerance measures. The DII has demonstrated strong internal consistency reliability in clinical and unselected samples (McHugh & Otto, 2011) as well as strong concurrent and discriminant validity and distinguishes clinical from non-clinical groups (McHugh & Otto, 2012).

Drug Use Motives Questionnaire (DUMQ). The DUMQ (Mueser, Nishith, Tracy, DeGirolamo, & Molinaro, 1995) is a 15-item self report inventory designed to provide an assessment of coping, social and enhancement motives for alcohol use (Cooper, Russell, Skinner, & Windle, 1992). We will use a modified DMQ to assess non-alcohol drug use motives (as utilized by Mueser et al., 1995) with the addition of 5 items to assess for use of opioid for pain coping.

Exit Interview. Participants will be asked to complete an exit interview with a study investigator after the completion of the treatment. Participants will be given the opportunity to share feedback on their experience with the treatment and will be asked how well the treatment addressed their needs. This will be audiotaped and transcribed for analysis.

Fagerstrom Test for Nicotine Dependence (FTND). The FTND (Heatherton, Kozlowski, Frecker, & Fagerstrom, 1991) will be used as a continuous measure of nicotine dependence. The FTND has shown good internal consistency, a single dimension factor structure, and positive relationships with degree of nicotine intake as assessed by saliva cotinine. FTND items are combined with other smoking history items in this study.

Hamilton Anxiety Rating Scale (HARS). The HARS (Hamilton, 1959) is an interviewer-administered measure of anxiety symptoms. The Structured Interview Guide for the HARS (Shear et al., 2001) was developed to improve the reliability of the HARS and will be used in this study. This will be the primary outcome measure for the study.

Homework Compliance. Both participants and clinicians will separately rate compliance with homework/skills practice on a weekly basis with a form adapted from an assessment of homework compliance developed by Primakoff, Epstein, & Covi (1986).

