Anxiety Sensitivity Index	X	X	X	X	X		X
Opioid Craving Scale	X	X	X	X	X		X
Overall Anxiety Symptom and Impairment Scale	X	X		X			X
Insomnia Severity Index	X			X			X
PANAS-Positive Affect	X		X	X			
Perseverative Thinking Questionnaire	X			X	X		X

Perceived Stress Scale		X		X	X	X	X
Distress Intolerance Index		X		X	X	X	X
Process							
Client Satisfaction Questionnaire			X	X			
Credibility and Expectancy Scale		3 & 7	X				
HW Completion		X					
Key Concepts Questionnaire	X			X		X	
Qualitative							
Exit Interview				X			
Behavioral							
Go/NoGo Task	X						
Psychophysiological/Biomarkers							
Saliva Samples ^b		X	X	X			
Menstrual Cycle Information ^b		X	X	X			
Stress Reactivity Paradigm	X			X			

Note. ^aBased on the primary presenting anxiety disorder, participants will complete a self-report measures specific to that diagnosis.

^bOnly female participants will be asked to provide saliva samples given that we are examining fluctuations in ovarian hormones.

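### The exit interview is tied to completing treatment and is not expressly offered to early leavers, so the qualitative evidence on acceptability (Aim 1) may under-represent them

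*Combined protocol and SAP*

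**What the plan says.** Aim 1 (section II) expects ICBT to be feasible and acceptable, "as assessed by the ability to recruit and retain the target population and participant self-report of treatment satisfaction". Section VI states the analysis: "Measures of patient satisfaction will be considered along with qualitative exit interviews to determine the acceptability of the treatment".

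The interview is timed in two places. Section V: "Qualitative exit interviews will be conducted at the completion of treatment". Section V.4.1, Exit Interview: "Participants will be asked to complete an exit interview with a study investigator after the completion of the treatment". Its stated purpose includes learning which sessions helped least and what could be improved.

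For satisfaction, the CSQ entry in section V.4.1 reads: "an 8-item self-report measure of treatment satisfaction, will be administered at post-treatment". In Table 1 the row for the "Client Satisfaction Questionnaire" carries two marks, not one. The Credibility and Expectancy Scale is given during treatment: "This measure will be administered at sessions 3 and 7 as a measure of feasibility".

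On participants who leave treatment, section VI promises "vigorous outreach, including to any participants who elect to dropout of treatment prior to completion". Section V schedules the week 12 assessment for all participants, and section V.3 allows it by phone, with the loss of some unspecified data points.

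**The concern.** A participant who stops ICBT at session 3 or 4, perhaps because the exposure work was too hard, is an informative witness on acceptability. If the interview follows completion of treatment, that person is not interviewed. If the reason for stopping is not recorded either, the trial can count such people but cannot tell dislike of the treatment from relapse, moving away or scheduling trouble.

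The stake is the qualitative half of the acceptability conclusion. An interview meant to find what should be improved would draw mainly on people who had reached the end. If stopping differed between ICBT and IDC, the interview samples would also differ in kind between the arms.

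**Working it through.** The plan gives no numerical target or precision for acceptability, so there is no figure of its own to reproduce. The power statement in section VI concerns Aim 2 and does not bear on this point. The check is first a reading of the text, then a short calculation of scale.

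**1. What reaches a participant who stops at session 3 or 4**

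- *Exit interview:* sections V and V.4.1 place it at or after completion of treatment. Neither describes a version for early leavers, and no phone interview is mentioned.
- *Reason for stopping:* not collected in any section. Two consecutive weeks of missed sessions trigger a review of the participant's appropriateness for the study (section VII), but no reason is recorded for analysis.
- *CSQ at week 12:* available, because the visit is for all and dropouts are pursued. The rating would come 12 − 4 = 8 to 12 − 3 = 9 weeks after stopping. Section V.3 does not say whether the CSQ survives a switch to phone.
- *CSQ at mid-treatment:* missed, since the participant has left before week 6.
- *Credibility and Expectancy Scale:* the session 3 rating may exist, but it measures expected benefit and credibility, not satisfaction.

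A participant who stops after week 6 differs in one respect: a mid-treatment CSQ may already be on file.

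**2. CSQ timing in Table 1**

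The table is broken in the text available, so this reading is probable, not certain. Section V.4.1 fixes the PANAS positive-affect scale at baseline, mid-treatment and post-treatment. The last two PANAS marks stand in the same positions as the two CSQ marks, which puts the CSQ at mid- and post-treatment. The single exit interview mark falls in the post-treatment position. The text entry for the CSQ names post-treatment only, so text and table disagree.

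**3. Scale**

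Inputs from the documents: N = 54; loss to follow-up expected to be no more than 10%, with up to 20% allowed for (section VI). Assumed: 1:1 allocation, so 54 / 2 = 27 in ICBT.

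- Participants: 54 × 0.10 = 5.4 and 54 × 0.20 = 10.8 overall; 27 × 0.10 = 2.7 and 27 × 0.20 = 5.4 in ICBT.
- Bias of an observed mean = share missing × (mean of observed − mean of missing). The gap is not in the documents; 0.5 to 1.0 SD is assumed.
- 10% missing: 0.10 × 0.5 = 0.05 SD to 0.10 × 1.0 = 0.10 SD.
- 20% missing: 0.20 × 0.5 = 0.10 SD to 0.20 × 1.0 = 0.20 SD.
- 30-40% missing (assumed, if outreach or phone contact fails to capture the CSQ): 0.30 × 0.5 = 0.15 SD to 0.40 × 1.0 = 0.40 SD.
- If the gap is zero, so is the bias; if early leavers were more satisfied, the sign would reverse.

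These figures apply to the CSQ. For the interview, the literal text leaves out every early leaver, whatever the follow-up rate.

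**The case against.** The strongest reply is that completion of treatment can mean the end of the 12-week period. Section V.4.1 says participants in general will be asked, Table 1 appears to put the interview at the post-treatment visit, and that visit is for all. On this reading early leavers are not excluded. The reply stands as far as it shows ambiguity. It does not show that they are included: no sentence says so, and staff following the literal wording could leave them out.

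A reader might go further and infer that acceptability as a whole is judged by those who stayed and is therefore biased upward. The documents do not support that. The week 12 CSQ is sought from dropouts, with a phone option; Table 1 probably adds an earlier CSQ; and retention is itself an Aim 1 criterion, so stopping counts against the treatment directly. An upward direction is plausible, but no satisfaction difference is given. The 10-20% in section VI is loss to follow-up; no rate of treatment stopping is stated.

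It might also be inferred that the manual will be revised for Stage 2 without this evidence. Section VI says only that the results would inform power calculations for that trial.

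Session-by-session adverse event enquiry (section IX.1) and the review after missed sessions mean that distress would not go unseen. Neither yields a view of the treatment or a reason for leaving. Intent-to-treat analysis and mixed models use partially observed outcomes, but cannot recover an interview that was never offered.

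**Conclusion.** The point holds for the interview and only weakly for the CSQ. As written, the plan neither offers the exit interview to participants who stop early nor records why they stopped, so the interview evidence may under-represent those who found the treatment unacceptable. For the CSQ, what remains is a late rating for those who leave before week 6, an unresolved phone question, a mismatch between text and table, and no stated handling of missing satisfaction data. Its numerical effect is probably modest: 0.05-0.20 SD at 10-20% missing, under the assumed gap of 0.5-1.0 SD and with follow-up loss used only as a stand-in for missing CSQ scores. Neither size nor direction can be taken from the documents. Aim 2 is untouched. This is a worthwhile, inexpensive improvement, not a flaw that defeats the design.

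**What to change.** - In section V and the Exit Interview and CSQ entries of section V.4.1, offer both to every randomised participant who attended at least one session, at the end of treatment or soon after stopping, by phone if needed.
- Record the main reason for stopping.
- Make the CSQ entry in section V.4.1 and its row in Table 1 agree, and say in section V.3 whether the CSQ can be taken by phone.
- In section VI, report the number responding, the satisfaction scores and the interview themes by arm and treatment-completion status, next to retention, and base the Aim 1 conclusion on all of them.

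The cost is a few sentences of protocol text and a few extra short interviews. The locator procedures, phone contact and $10 interview payment are already in section V.3. Some early leavers will decline, so the selection is reduced, not removed; reporting the number responding makes the remainder visible.
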